### 3.1    **Study design**

This non-confirmatory study will be conducted in 2 cohorts using a one-sequence two-period design to compare SOM230 vs. Placebo. Following observed efficacy and safety signals in Cohort 1 with the 1.5 mg dose, cohort 2 of the study assessing efficacy of a lower SOM230 dose (0.9 mg) may be considered.

Two consecutive attacks will be treated: first attack will be treated with placebo (Period 1) and the following attack will be treated with SOM230 (Period 2). Approximately 30 patients will be enrolled in Cohort 1 to receive Placebo s.c. single dose in Period 1 then SOM230 1.5 mg s.c., a single dose in Period 2. Each study cohort will consist of a 21 day screening period, a baseline period of 3 days prior to the Baseline Visit, a treatment period (Period 1) lasting up to 3 days then a treatment period 2 of up to 3 days, followed by an end of study visit 3 days after study drug administration in Period 2. The subjects will have up to 5visits. Similarly, in Cohort 2 approximately 30 subjects will receive placebo s.c. single dose in Period 1 and SOM230 0.9 mg s.c., as a single dose in Period 2. Each subject will be instructed to self-administer (or assisted by a helper, or by medical staff if domiciled at a clinic) the study medications at the beginning of the CH attack (as early as possible; within 10 minutes of start of attack when pain is at least moderate). In case patient experiences CH attacks PRIOR to administering study treatment in Period 1 they can use 100% O2 or their conventional treatment to manage their acute attacks experienced before Period 1. If the subject does not have a headache attack in **72 hours post-baseline** or 72 hours post Period 1 treatment the subject will be excluded from the study. Subjects will be required to complete a patient diary to document the pain severity and pain relief before and after the administration of the study medication (**Figure 3-1**). In case the pain is not responding to the administered study drug after 30 minutes, subjects will be allowed to use only 100% oxygen as a rescue

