case of concomitant use of sumatriptan, and the relatively longer study period, patients will be allowed to only use 100% oxygen as rescue-medication, and a conventional randomized cross-over design seemed unsuitable. The use of placebo will allow unbiased assessment of the benefit of SOM230 using subjective endpoints. Consecutive assessment of the 1.5mg dose followed by assessment of low dose (0.9 mg s.c.) will provide cluster headache patients with a better chance of getting efficacious doses with a potential for earlier relief of pain and possibly a longer interval till the next attack. Inclusion of the two SOM230 dose levels in cohort 1 and cohort 2 will provide the opportunity to determine the dose response relationship and obtain initial estimates of the treatment differences in efficacy parameters.

Due to the medical condition, it is not possible to collect PK samples during an attack. Samples will therefore be collected during the visit following an attack after drug administration in each period.

Corporate Confidential Information

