## **6.9      Rescue medication**

Subjects will be allowed to use 100% oxygen as rescue medication during the study as described in [Section 7.1](#). If subjects require use of other rescue medication, they must contact the site immediately to be discontinued from the study. Every effort must be made to obtain study data for at least 24 hours after study medication has been administered. Use of rescue medication must be recorded on the Concomitant medications/Significant non-drug therapies CRF after start of study drug.

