## **6.10     Concomitant treatment**

Subjects are not to take any other medication to treat cluster headaches other than study medication. Concomitant treatment will be limited to only treat adverse experiences not associated with cluster headaches. Patients will be allowed to take 100% oxygen as rescue medication during the study starting 30 minutes after study drug administration.

In case patient experiences CH attacks PRIOR to administering study treatment in Period 1 they can use 100% O2 or their conventional treatment to manage their headache attacks experienced before Period 1.

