# **7        Discontinuation and study completion**

## **7.1      Discontinuation of study treatment**

Subjects will be discontinued from the study if the subject receives additional treatment for the CH pain other than 100% oxygen after subject has had no relief of pain for at least 30 minutes following study medication administration. However data collected up to this point will be included in the assessment.

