## **11.1 Analysis sets**

For all analysis sets, subjects will be analyzed according to the study treatment received.

The safety analysis set will include all subjects that received any study drug.

The PK analysis set will include all subjects with available PK data and no protocol deviations with relevant impact on PK data.

The efficacy/PD analysis set will include all subjects that received any study drug and had no protocol deviations with relevant impact on efficacy/PD data.

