Subjects will be required to complete a patient diary to document the pain severity and pain relief before and after the administration of the study medication. In case the pain is not responding to the administered study drug after 30 minutes, subjects will be allowed to use only 100% oxygen or sumatriptan as a rescue management. If applicable and feasible, subjects in Period 1 may return to the study center for follow-up within 24 hour post treatment administration. The subjects will have a follow-up within 24 hours of the study drug administration in Period 2 where a PK sample will be collected, with a second PK sample collected to 1 to 2 hours after the 1st PK sample. In case the follow-up visit in Period 2 falls on a weekend, a window of up to 48 hours may be considered.

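### The SAP's both-periods efficacy set drops placebo failures discontinued for non-oxygen rescue, whose 30-minute placebo result the protocol keeps; the effect is small, and whether it arises depends on a rescue rule on which the documents differ

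*SAP*

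**What the plan says.** **Analysis set.** Protocol 11.1: "The efficacy/PD analysis set will include all subjects that received any study drug", provided no deviation affects the efficacy data. SAP 4 keeps the deviation condition but requires study drug in both periods.

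**Rescue.** SAP 1.4: "subjects will be allowed to use only 100% oxygen or sumatriptan as a rescue management". SAP 6.1.2, 6.1.3, 6.1.3.1, 6.1.4 and 6.2.1.3 also name sumatriptan. The supplied protocol differs:
- Section 3.1: "subjects will be allowed to use only 100% oxygen as a rescue" measure. Section 3.2 repeats this ("patients will be allowed to only use 100% oxygen as rescue-medication") and gives the reason, which is to keep adverse-event evaluation clear of sumatriptan.
- Section 6.10: "Subjects are not to take any other medication to treat cluster headaches other than study medication", with oxygen as the exception from 30 minutes after dosing.
- Section 6.9: "If subjects require use of other rescue medication, they must contact the site immediately to be discontinued from the study".
- Section 7.1: "Subjects will be discontinued from the study if the subject receives additional treatment for the CH pain other than 100% oxygen". It then adds: "However data collected up to this point will be included in the assessment".

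**Timing of discontinuation.** Section 6.9 has the subject contact the site at once. Footnote 2 to Protocol Table 8-1 instead aims to discontinue a subject who needs standard treatment after 24 hours from dosing.

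**Model.** Protocol 11.4.2 specifies a repeated-measures logistic model with subject as a random effect. SAP 6.1.3 uses the 30-minute data alone, without a subject effect. SAP 6.1.3.1 restores that effect in a sensitivity analysis over all time points, run only if the primary result is significant.

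**Version.** SAP 1.2 says the SAP was built on protocol v04, incorporating Amendment 04.

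**The concern.** The first attack is always treated with placebo and the second with SOM230. Someone discontinued between the two attacks has a placebo value and no SOM230 value. If the reason was non-oxygen rescue for the Period 1 attack, that placebo value is very probably a failure. The both-periods rule then removes subjects in a way that depends on the primary outcome under placebo, although the protocol says to use their data.

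The rescue rule decides whether this route exists. If sumatriptan is permitted, as in SAP 1.4, a user stays in the study, receives SOM230 and remains in the set, unless deviation code COMD01 is applied to the pair. If oxygen alone is permitted, the user is discontinued and may never reach Period 2.

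At stake is the placebo-adjusted response rate, which Protocol 11.6 compares with a 30-point threshold for clinical relevance. The set-to-missing rule does not repair the loss, because it concerns measurements within the set. Nor does the borrowing described in SAP 6.1.3.2, because a model with one time point and no subject effect has nothing to borrow through.

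**Working it through.** **Inputs.** From Protocol 11.6: placebo response 30%, SOM230 response 72%, correlation 0.25, 23 evaluable subjects, 20% drop-out, about 30 enrolled per cohort. The share u of placebo failures lost through non-oxygen rescue is not in the documents; 5 to 30% is assumed.

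**The plan's own figures.** Enrolment: 23 / 0.80 = 28.75, so 29, against about 30 planned. Power: exact enumeration of the paired table at n = 23, requiring an observed difference of at least 30 points and a one-sided 90% Wald criterion, gives 88.2% against the stated 80% or so. Raising the threshold by one subject, to 8/23, gives 79.3%. The protocol does not describe its simulation estimator and its figure is the more cautious one, so this is no evidence of error. Nothing below relies on it.

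**Paired cells.**
- Both respond: 0.30 × 0.72 + 0.25 × √(0.30 × 0.70 × 0.72 × 0.28) = 0.2674
- SOM230 only: 0.72 − 0.2674 = 0.4526
- Placebo only: 0.30 − 0.2674 = 0.0326
- Neither: 0.2474
- SOM230 response among placebo failures: 0.4526 / 0.70 = 0.647

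**Expected results per 30 subjects.** There are 9 placebo responders, 21 placebo failures and 21.6 SOM230 responders. With k = 21u lost after Period 1:
- both-periods set: placebo rate 9 / (30 − k); difference (12.6 − 0.647k) / (30 − k)
- Protocol 11.1 set with no subject effect: (21.6 − 0.647k) / (30 − k) − 0.30

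| u | k | Placebo rate, both-periods set | Difference, both-periods set | Difference, Protocol 11.1 set, no subject effect |
|---|---|---|---|---|
| 0% | 0 | 30.0% | 42.0 | 42.0 |
| 5% | 1.05 | 31.1% | 41.2 | 42.3 |
| 10% | 2.10 | 32.3% | 40.3 | 42.6 |
| 20% | 4.20 | 34.9% | 38.3 | 43.2 |
| 30% | 6.30 | 38.0% | 36.0 | 44.0 |

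**Adding the subject effect.** A random-intercept logistic model fitted by quadrature to the expected counts on the Protocol 11.1 set returns 30.0%, 72.0% and a difference of 42.0 points at every u in the table. With two binary values per subject, its two means and one variance reproduce the paired table, so placebo-only subjects are handled correctly when the missing SOM230 value depends only on the placebo result. This check omits the severity and headache-type covariates.

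**Direction.** If lost subjects would respond to SOM230 at rate q, the both-periods difference (12.6 − qk) / (30 − k) exceeds 0.42 only when q < 0.42. The protocol's assumptions imply 0.647. With no drug effect (30% in both periods), the both-periods set gives −1.7 points at u = 10% and −6.0 at u = 30%.

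**Chance of observing at least 30 points.** With 24 pairs retained after exclusion, exact enumeration gives 83, 81, 79, 73 and 66% at u = 0, 5, 10, 20 and 30%. These figures hold the number of pairs fixed, so they show the effect of the shifted rates alone.

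**The case against.** **The rescue conflict may be only a version mismatch.** This stands. If v04 allowed sumatriptan, this route to exclusion closes. A reader might infer that the SAP misstates its own protocol, but the documents do not establish that, because the supplied protocol's version is not visible. The SAP's rules for measurements after sumatriptan would also serve for protocol deviators; only the sentence in SAP 1.4 grants permission. The difference between the two set definitions remains either way, unless v04 changed that as well.

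**The subject may be dosed before being discontinued.** This stands in part. Eligible patients average 2 to 6 attacks a day, outpatients hold the drug at home, and the Table 8-1 footnote points to discontinuation after 24 hours. The next attack could therefore be treated with SOM230 first. Section 6.9 points the other way.

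**Not every lost subject is a placebo failure.** This stands. The same footnote covers recurrent attacks, so a 30-minute responder could also leave. The placebo rate rises generally, not always.

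**The uptake is assumed.** This stands. Protocol 3.2 expects mainly non-sumatriptan users, which favours the low end. The 20% drop-out allowance may already cover the lost numbers; it does not address the selection.

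**A both-periods set suits a within-patient comparison.** That is a fair reason to keep it as one analysis. It does not account for leaving out data that Protocol 7.1 says to use.

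Two stronger readings should be resisted. Same-attack rescue does not contaminate the 30-minute value, because the plan permits it only after 30 minutes. And the set does not flatter SOM230: under the protocol's assumptions it does the reverse.

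**Conclusion.** The point holds as a minor one. The SAP's efficacy set is narrower than the protocol's, and under the protocol's oxygen-only rule the narrowing can remove placebo failures because of their outcome. The estimated effect would fall by 0.8 to 1.7 points at 5 to 10% loss (about one or two subjects per cohort) and by up to 6.0 points at 30%.

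This rests on the Protocol 11.6 response rates and correlation, on an assumed uptake, on discontinuation before the next attack, on lost subjects responding to SOM230 like other placebo failures, and on no carry-over. The bias generally runs against the drug, and the study is non-confirmatory, so the realistic harm is a somewhat understated signal. The documents do not show that sumatriptan rescue took place or that any subject was lost this way.

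**What to change.** Before database lock:

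1. Compare SAP 1.4 with protocol v04. Correct the SAP to oxygen only or, if sumatriptan was in fact allowed, align Protocol 3.1, 3.2, 6.9, 6.10 and 7.1. Settle whether discontinuation is immediate (6.9) or after 24 hours (Table 8-1, footnote 2).
2. Run the 30-minute logistic regression on the Protocol 11.1 set, keeping Period 1 data of subjects discontinued for non-oxygen rescue, with subject as a random effect as in Protocol 11.4.2. Report it beside the both-periods analysis, not conditional on significance.

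The cost is a wording change, one flag and one extra table from data already collected, with no added patients or visits. The random-effect fit may be unstable at this size, and it relies on missing at random, which the SAP already assumes. The subject effect should not be left out: without it the wider set overstates the effect by about 0.3 to 2.0 points (42.3 − 42.0 to 44.0 − 42.0). If the fit fails, a simple fallback without covariates is: placebo rate × SOM230 response among placebo responders + (1 − placebo rate) × SOM230 response among placebo failures − placebo rate.

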**Figure 1.4-1 Study Design – Cohorts 1 and 2**

## 2 First interpretable results (FIR)

First interpretable results (FIR) will be provided for this trial.  
Corporate Confidential Information

## 4 Statistical methods: Analysis sets

For all analysis sets, subjects will be analyzed according to the study treatment received.

The safety analysis set will include all subjects that received any study drug.

The PK analysis set will include all subjects with available PK data and no protocol deviations with relevant impact on PK data.

The efficacy/PD analysis set will include all subjects that received study drug in both periods and had no protocol deviations with relevant impact on efficacy/PD data.

The analysis sets and protocol deviation codes are related as follows:

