### 4.1 Inclusion criteria

1. Subject is male or female age 18-65 inclusive.
2. Written informed consent must be obtained before any assessment is performed.
3. Subjects must have established diagnosis of episodic cluster headaches (CH) or chronic CH, averaging 2-6 headache attacks per day each lasting at least 45 minutes without treatment, not to exceed 6 attacks per day within the last year.
4. Able to communicate well with the investigator, to understand and comply with the requirements of the study, as well as accepting NOT to share any study information through social media during their participation in the study.
5. Subject is able to self-inject medication subcutaneously or have the assistance of a helper on an out-patient basis, if subject is not domiciled in a clinic for the study.

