**Table 4-1 Protocol deviation codes and analysis sets**

Category Deviation code	Text description of deviation	Data exclusion
Subjects are excluded from all (safety) analysis in case of these PDs:		
12	Written ICF not obtained	Exclude subject completely from all (safety) analysis sets
Subjects are excluded from PK analysis in case of these PDs:		Exclude subject from PK analysis set

*TRTD01      Study drug dosing error or incorrect treatment administered.*

---

Subjects are excluded from PD analysis in case of these PDs:		Exclude subject from PD analysis set
COMD01	Used prohibited treatment within 24 hours before receipt of study drug and within the first 30 minutes post dose.	
TRTD01	Study drug dosing error or incorrect treatment administered. Predose severity of CH is not at least moderate at one of the periods (unless there was a diary entry error)	Corporate Confidential Information

If updates to this table are needed, an amendment to the SAP needs to be implemented prior to DBL

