#### **6.1.3.2 Handling of missing values/censoring/discontinuations**

Assuming missing at random, a subject with missing value at a time point will still contribute to the estimation of the treatment effect at that particular time point as the likelihood-based repeated measures analysis borrows information from non-missing values of this subject and other subjects.

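### The SAP primary model treats each subject's two 30-minute records as independent, which discards the within-patient comparison; separately, SAP 4 narrows the Protocol 11.1 efficacy set without a visible reason

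*SAP*

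**What the plan says.** **Model.** Protocol 11.4.2 specifies a logistic regression over time with a random subject effect. Protocol 3.2 justifies the one-sequence design partly by the power gained from comparing each patient with himself or herself. SAP 6.1.3 instead uses the 30-minute data alone, with baseline severity, CH type and dose as fixed effects and no subject term. The model with a subject effect moves to SAP 6.1.3.1, where it is run only if the primary result is significant. McNemar at 30 minutes (SAP 6.1.4) is optional.

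**Missing data.** SAP 6.1.3.2, placed under the primary analysis, says that "a subject with missing value at a time point will still contribute to the estimation of the treatment effect at that particular time point", because a repeated-measures likelihood draws on the subject's other values.

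**Analysis set.** Protocol 11.1: "The efficacy/PD analysis set will include all subjects that received any study drug and had no protocol deviations with relevant impact on efficacy/PD data". SAP 4: "The efficacy/PD analysis set will include all subjects that received study drug in both periods and had no protocol deviations" of relevant impact. SAP Table 4-1 also removes a subject from the PD set if "Predose severity of CH is not at least moderate at one of the periods".

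**Ways to be dosed only once.** Protocol 6.9: "If subjects require use of other rescue medication, they must contact the site immediately to be discontinued from the study". Protocol 7.1 discontinues such a subject and adds: "However data collected up to this point will be included in the assessment". Under Protocol 3.1, a subject with no attack within "72 hours post Period 1 treatment the subject will be excluded from the study".

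**The concern.** The two records of one subject are correlated; the protocol itself plans on 0.25. A model that treats them as independent attaches the wrong standard error to the primary comparison. With positive correlation the error is conservative: intervals are too wide, and the precision the design was chosen to obtain is lost. With about 23 evaluable subjects per cohort that loss counts.

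The analysis set is a second matter. Every once-dosed subject is a placebo-only subject. A rule that requires both doses removes that subject's 30-minute placebo result from the primary analysis, and the reason for not reaching Period 2 may be linked to that result. Non-permitted rescue after no relief is one such link. The primary comparison would then be made in a population narrower than the one the protocol names, with membership that can depend on one of the two outcomes being compared.

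**Working it through.** **Inputs (Protocol 11.6).** Placebo response 0.30, SOM230 response 0.72, difference 0.42, correlation 0.25, 23 evaluable subjects, 20% drop-out, about 30 enrolled. The loss fractions in step 4 are assumptions; the documents give none.

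**1. The plan's own figures.** Enrolment: 23 / 0.80 = 28.75, so 29, consistent with about 30. The stated power of about 80% does not reproduce exactly. Exact enumeration of the paired outcomes, requiring an estimated difference of at least 30 points and a one-sided p of at most 0.10, gives 88.2% at correlation 0.25 and 84.8% at zero correlation. The analysis model used in the protocol's simulation is not stated, and nothing below depends on the 80%.

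**2. Joint cells (placebo, SOM230).**
- Both respond: 0.30 × 0.72 + 0.25 × √(0.30 × 0.70 × 0.72 × 0.28) = 0.2674
- Placebo only: 0.30 − 0.2674 = 0.0326
- SOM230 only: 0.72 − 0.2674 = 0.4526
- Neither: 0.2474

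**3. Standard error with and without pairing (n = 23, before covariates).**
- Paired: √[(0.0326 + 0.4526 − 0.42²) / 23] = √(0.3088 / 23) = 0.116
- Treated as independent: √[(0.30 × 0.70 + 0.72 × 0.28) / 23] = √(0.4116 / 23) = 0.134
- Ratio 1.15, so about 15% larger.
- Approximate coverage of a nominal 90% interval: 2Φ(1.645 × 1.155) − 1 = 2Φ(1.90) − 1 ≈ 0.94. Simulation from these cells for the unadjusted log odds ratio agrees: about 94% for the SAP 6.1.3 model, against about 89% with subject-clustered errors and no small-sample correction.

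**4. Shift from the both-periods set.** Let f and g be the shares of placebo non-responders and responders lost before Period 2. Multiply the non-responder cells by (1 − f) and the responder cells by (1 − g), then rescale. The expected difference is

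[0.4526(1 − f) − 0.0326(1 − g)] / [0.70(1 − f) + 0.30(1 − g)]

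| Loss | Expected difference, points |
|---|---|
| f = g | 42.0 |
| f = 0.05, g = 0 | 41.2 |
| f = 0.10, g = 0 | 40.3 |
| f = 0.20, g = 0 | 38.3 |
| f = 0, g = 0.05 | 42.8 |
| f = 0, g = 0.10 | 43.6 |

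The 5% and 10% rows correspond to about 1 and 2 of 30 subjects when non-responders are lost (0.70 × 30 = 21), and to one subject or fewer when responders are lost (0.30 × 30 = 9).

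**5. Changing the set alone does not cure this.** At f = 0.20 the any-study-drug set analysed with the SAP 6.1.3 model sets SOM230 at 73.2% against placebo at 30.0%, a difference of 43.2: a smaller bias in the other direction. A model that links the periods recovers 42.0 if loss depends only on the placebo result: 0.30 × (0.2674 / 0.30) + 0.70 × (0.4526 / 0.70) = 0.72.

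**6. A random intercept at one time point is fragile.** The placebo-only cell is empty with probability (1 − 0.0326)^30 = 0.37 in a cohort of 30, and the variance of the random effect then has no finite maximum-likelihood estimate.

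**The case against.** A set of subjects dosed in both periods is a defensible choice for a paired one-sequence design, and the study is declared non-confirmatory. At modest loss the shift in step 4 is small beside a standard error of 11.6 points. The pairing is not absent from the SAP: McNemar and the 6.1.3.1 model both keep it. Parts of the SAP are redacted, including text beside the predose-severity entry in Table 4-1, and the SAP cites Protocol v04 while the version of the supplied protocol is not visible. A reason for the narrower set may exist.

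All of this stands, and it limits the set issue to a reconciliation. It does not rescue the primary model: one paired analysis is optional and the other depends on a significant primary result.

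Some stronger readings are tempting but unsupported:
- *That the 6.1.3 model cannot use once-dosed subjects, contrary to 6.1.3.2.* The set rule bars them, not the model, which could take a lone placebo record. SAP 6.1.3.2 speaks of a missing value at a time point and never mentions once-dosed subjects.
- *That the set favours SOM230, or works against it.* Both directions are possible. If the whole 20% allowance fell on placebo non-responders the difference would be 36.3, and if on responders 55.2. These are extremes, and the allowance is not confined to loss between periods.
- *That Protocol 11.1 certainly keeps every once-dosed subject.* Whether non-permitted rescue is an efficacy deviation, and whether exclusion from the study for want of an attack means exclusion from analysis, is not stated. The second route should be uncommon, since entry requires "averaging 2-6 headache attacks per day each lasting at least 45 minutes without treatment".
- *That no output will show the once-dosed subjects.* This cannot be established from a partly redacted SAP.

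**Conclusion.** The primary model is wrong as written for paired data. It departs from Protocol 11.4.2 and, at the planning values, inflates the standard error from 11.6 to about 13.4 points and gives about 94% coverage at a nominal 90%. These figures assume correlation 0.25, 23 complete pairs and no covariate adjustment. A reader might infer an inflated false-positive rate; with positive correlation the error runs the other way, towards lost precision. SAP 6.1.3.2 describes a property that only the conditional 6.1.3.1 model has.

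The change of analysis set is real and unexplained in the visible text. It allows selection on the placebo outcome, but the documents determine neither direction nor size, and a loss of 5–10% of either response group moves the expected difference by about 1 to 2 points. That calls for reconciliation and disclosure; it does not show a biased result. The extent of the rescue route cannot be judged while the protocol (oxygen only) and the SAP (oxygen or sumatriptan) disagree on permitted rescue.

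**What to change.** 1. **SAP 6.1.3.** Keep the logistic model but allow for two records per subject, for example by GEE or subject-clustered standard errors with a small-sample correction, and report the marginal placebo-adjusted rate with its 90% interval. Use a random-intercept fit only as a check. Make McNemar at 30 minutes a planned analysis.
2. **SAP 6.1.3.2.** Limit the borrowing statement to the 6.1.3.1 model.
3. **SAP 4.** Reconcile the set with Protocol 11.1 and 7.1. If the both-periods set stays primary, give the reason. Add a sensitivity analysis on the any-study-drug set with a model that links the periods within subject; clustered errors alone leave the 43.2 of step 5 unchanged. Add a table of Period 1 response and reason for not reaching Period 2 for once-dosed subjects.
4. **Rescue.** The protocol and SAP passages on permitted rescue must be reconciled.

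Cost: SAP wording, one sensitivity table and one short disposition table; no new data. Robust errors are slightly anti-conservative at this size without the correction (about 89% in step 3). The linked model relies on loss depending only on observed data. If loss also depends on the unseen Period 2 result, either set may be further from the truth, so both should be shown.
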